7.1.2 Premedication

No routine premedication (e.g. for nausea) or prophylaxis for hypersensitivity is required. For durvalumab, management of symptoms should take place as necessary (see Appendix II). Premedication is not expected to be required. See Appendix II with respect to premedication of patients that have had a prior < Grade 2 infusion-related reaction. Details of any premedication or concomitant medication given to manage or prevent adverse events should be recorded on the electronic case report form (eCRF).

7.1.3 Dose Levels

The following are dose levels for CFI-400945, which will be titrated according to the degree of toxicity:

DL+1 (escalation)	DL1	DL-1	DL-2
40 mg daily	32 mg daily	32 mg / 5 days per week (5 days on/2 days off)	32 mg / 3 days per week
Note: intermediate dose levels/schedules may be selected after review of data by CCTG and investigators.			

Durvalumab will be administered as a flat dose of 1500 mg for patients > 30 kg in weight. If patient weight falls to ≤ 30 kg, weight-based dosing at 20 mg/kg will be administered. No dose reductions are planned.

7.1.4 Patient Monitoring

Patients will be monitored before, during infusion and after the infusion of durvalumab. A 1-hour observation period is recommended after the first durvalumab infusion period. If no clinically significant infusion reactions are observed during or after the first cycle, subsequent observation periods can be at the discretion of the investigator (30 minutes is suggested).

Guidelines for management of infusion-related reaction are summarized in Appendix II.

All patients should be closely monitored according to guidelines in Section 5.0 and be advised to contact the treating centre in the case of significant toxicities.

7.1.5 Dose Modifications – CFI-400945

Doses will be reduced for hematologic and other adverse events. Dose adjustments are to be made according to the system showing the greatest degree of toxicity. Adverse events will be graded using the NCI Common Terminology Criteria for Adverse Events (CTCAE) (see Appendix V).

Reported and/or expected toxicities include, but are not limited to: amylase/lipase increases, neutropenia and leucopenia, febrile neutropenia fever and chills, infection, typhlitis/diarrhea, fatigue, increased liver function tests, nausea, vomiting, mucositis. The guidelines which follow outline dose adjustments for several of these toxic effects. If a patient experiences several adverse events and there are conflicting recommendations, please use the recommended dose adjustment that reduces the dose to the lowest level. Doses should only be modified for toxicity related to CFI-400945.

Diarrhea > Grade 1 is not a common toxicity of CFI-400945. Patients who experience diarrhea should be carefully evaluated for possible immune mediated colitis and managed accordingly.

Following any interruption of dosing for toxicity as described below, CFI-400945 should not be restarted until ANC $\geq 1.5 \times 10^9/L$ and platelets $\geq 100 \times 10^9/L$ and resolution of all drug related toxicity to \leq grade 2.

Table 1. Guidelines for CFI-400945 Dose Modifications for Neutropenia:

ANC (for dosing during cycle AND worst in prior cycle)	Cycles	Dose and management ^{1,3,4}
$\geq 1.5 \times 10^9/L$	All	No change. Note: If $\geq 1.5 \times 10^9/L$ for cycles 2 and 3 (or any 2 cycles after cycle 1) despite continuous oral dosing and having received at least 90% of planned doses ² : may escalate 1 DL
$1.0 \times 10^9/L - <1.5 \times 10^9/L$	All	Hold ⁴ until $\geq 1.5 \times 10^9/L$. No change in dose for next cycle.
Inability to receive at least 75% of planned dose within prior cycle	All	Hold ⁴ until $\geq 1.5 \times 10^9/L$.
$<1.0 \times 10^9/L$ (with no fever) <5 days ⁵		Reduce 1 DL
$<1.0 \times 10^9/L \geq 5$ days or febrile neutropenia	Cycle 1	Discontinue ⁶
	Other cycles	Hold ⁴ until $\geq 1.5 \times 10^9/L$. Reduce 2 DL
1. Hold if ANC $< 1.5 \times 10^9/L$; do not restart or start next cycle until ANC $\geq 1.5 \times 10^9/L$. 2. May also re-escalate after a prior dose reduction providing no febrile neutropenia and growth factors were not required and same conditions are met. 3. If Grade 3 or 4 ANC, CBC monitoring is required twice weekly for at least one full cycle after last event. 4. From Cycle 3 onward, CCTG may be contacted for an exemption to continue dosing if ANC $\geq 1.2 \times 10^9/L$. If cannot restart dosing within 21 days, discontinue. 5. If grade 3 neutropenia occurs in Cycle 3 onwards, contact CCTG to discuss option of no DL reduction. 6. Consult CCTG for clarification for borderline values in asymptomatic patients.		

Table 2. Guidelines for CFI-400945 Dose Modifications for Other Toxicity

Worst Toxicity	Management/Action	Dose of CFI-400945 when re-started*
Hematologic		
Grade 1 or 2 thrombocytopenia	No action. If grade 2, increase surveillance with twice weekly CBC for 2 cycles provided no further dose modification needed	No change
Grade 3 thrombocytopenia	Hold until $\geq 100 \times 10^9/L$	Reduce by 1 DL AND increase surveillance with twice weekly CBC for at least 2 cycles
Thrombocytopenic bleeding	Hold and treat, increase surveillance with twice weekly CBC	Reduce by 2 DL or discontinue, AND increase surveillance with twice weekly CBC for at least 2 cycles
Non-Hematologic**		
Grade 2 AST and/or ALT AND Grade 2 bilirubin	Discontinue	Discontinue
Hy's Law (AST or ALT $\geq 3 \times$ ULN AND total bilirubin $\geq 2 \times$ ULN)	Discontinue	Discontinue
Diarrhea Grade 2	Hold until immune mediated diarrhea excluded (or treated) and until recovered to \leq grade 1	Restart without dose reduction
Other Grade 3	Hold until \leq grade 2	Reduce by 1 DL
Other Grade 4	Discontinue	Discontinue
* If CFI-400945 cannot be restarted within 21 days, discontinue permanently.		
** Despite adequate supportive care.		

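### Table 2 lets CFI-400945 restart at grade 2 after grade 3 diarrhea, but requires grade 1 or less after grade 2 diarrhea

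*Combined protocol and SAP*

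**What the plan says.** Section 7.1.5, Table 2, governs CFI-400945 for toxicity other than neutropenia. The reader enters it by the worst grade reached.

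- **Worst grade 2 diarrhea.** The action is "Hold until immune mediated diarrhea excluded (or treated) and until recovered to" grade 1 or less. The restart dose is given as "Restart without dose reduction".
- **Worst grade 3 diarrhea.** There is no row for this. The catch-all row for other grade 3 non-hematologic toxicity holds the drug until grade 2 or less and restarts it one dose level lower.
- **Worst grade 4 diarrhea.** The corresponding grade 4 row stops the drug.

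Two footnotes apply to the diarrhea rows: "If CFI-400945 cannot be restarted within 21 days, discontinue permanently" and, for non-hematologic toxicity, "Despite adequate supportive care".

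The text above the tables adds a general restart rule: "Following any interruption of dosing for toxicity as described below, CFI-400945 should not be restarted until ANC" and platelets reach stated levels, with "resolution of all drug related toxicity to" grade 2 or less. The same text says "Patients who experience diarrhea should be carefully evaluated for possible immune mediated colitis and managed accordingly" and "Doses should only be modified for toxicity related to CFI-400945".

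**The concern.** A dose-modification table should not ask for less recovery after a worse event. By giving diarrhea its own row, the sponsor set a recovery standard stricter than the general rule: while diarrhea is at grade 2, CFI-400945 stays off. Because the row stops at grade 2, a patient whose diarrhea went on to grade 3 loses that protection. No reason is given for the difference.

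Section 7.1.5 lists typhlitis/diarrhea among the reported or expected toxicities of CFI-400945, and section 3.1.3 lists diarrhea among the common related events in phase I. At stake is the safety of individual patients who resume a drug that may be causing the diarrhea before it has settled. Sites may also handle the same situation differently.

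**Working it through.** The plan gives no figure to reproduce. The check sets the rows side by side and then looks for any other rule that removes the mismatch.

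**Step 1: rows compared (7.1.5, Table 2)**

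| Worst diarrhea grade | Highest grade at restart | Immune cause excluded or treated, as a row condition | Restart dose |
|---|---|---|---|
| 2 | 1 | Yes | Unchanged |
| 3 | 2 | No | Down one level |
| 4 | No restart | Not applicable | Not applicable |

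If the catch-all row were read as excluding diarrhea, only the general restart sentence would be left for grade 3. It also allows restart at grade 2, so the result is the same.

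**Step 2: weekly dose permitted while diarrhea is still grade 2 (dose levels from 7.1.3)**

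- DL+1: 7 × 40 = 280 mg
- DL1: 7 × 32 = 224 mg
- DL-1: 5 × 32 = 160 mg
- DL-2: 3 × 32 = 96 mg

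After worst grade 3, with the one-level cut:

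- from DL+1, 224 mg (56/280 = 20.0% lower)
- from DL1, 160 mg (64/224 = 28.6% lower)
- from DL-1, 96 mg (64/160 = 40.0% lower)

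After worst grade 2 the permitted dose is 0 mg.

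**Step 3: could another rule close the gap?**

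- The colitis evaluation in 7.1.5 and the general guidance in 7.1.7 ask for work-up and treatment. Neither sets a recovery grade for restarting CFI-400945.
- The conflict rule in 7.1.5 concerns several adverse events and picks the lowest dose level. It does not pick a recovery grade for one event.
- The linked hold in 7.1.1 acts through durvalumab. Durvalumab starts in cycle 2, so in cycle 1 there is none to hold. Under section 10.2 a patient who has stopped durvalumab for toxicity may continue CFI-400945 alone, and again there is none to hold.
- The next-cycle rule in 7.1.6 refers to Appendix II and governs the start of a cycle. It does not govern the day 15 dose within cycle 1.
- Appendix II is only a link, so its thresholds cannot be checked.
- The supportive-care footnote applies to both rows and leaves their order unchanged.

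**Step 4: cycle 1 example.** CFI-400945 is given on days 1-7 and 15-21. Suppose diarrhea peaks in days 1-7 and is still grade 2 on day 15, with blood counts adequate. If the peak was grade 3, the second week may be given at DL-1: 5 × 32 = 160 mg, assuming the five-day schedule is applied to that week. If the peak was grade 2, nothing is given.

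**Step 5: how many patients?** The protocol states no grade 3 diarrhea rate at 32 mg and calls diarrhea above grade 1 uncommon with this drug. I assume a rate p of 2% to 10%. Expected cases are n × p, and the chance of at least one case is 1 − (1 − p)^n. Section 3.1.4 reports 5 + 6 + 8 = 19 patients already enrolled at 64, 48 and 40 mg. Whether they count towards the 28 is not stated; if they do, 28 − 19 = 9 remain.

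| Assumed p | Expected, n = 28 | At least one, n = 28 | Expected, n = 9 | At least one, n = 9 |
|---|---|---|---|---|
| 2% | 0.56 | 43.2% | 0.18 | 16.6% |
| 5% | 1.40 | 76.2% | 0.45 | 37.0% |
| 10% | 2.80 | 94.8% | 0.90 | 61.3% |

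These are cases of grade 3 diarrhea. Patients actually restarted at grade 2 would be a subset.

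**The case against.** The best defence is that the two rows do different jobs. The grade 2 row reads as a diagnostic pause: rule out or treat colitis, let the patient recover, resume the full dose. The grade 3 row is the ordinary toxicity rule with a dose cut. A tighter recovery grade with full dose, against a looser grade with reduced dose, could be a deliberate trade-off. The reduction is a real offset, but it changes the dose and not the recovery required, and the protocol does not present it as a trade-off.

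A second argument is that the problem corrects itself, because a patient restarted with grade 2 diarrhea could be held again under the grade 2 row. The table does not say over what period the worst grade is counted, so a clinician might do this. But a rule that permits a restart and then calls for an immediate hold contradicts itself.

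Third, the dangerous case of immune colitis is largely handled elsewhere once durvalumab has started, through 7.1.1, 7.1.5, 7.1.6 and 7.1.7. That stands. The missing immune-exclusion condition in the grade 3 row is therefore secondary, and the net threshold from cycle 2 onward cannot be settled without Appendix II. The recovery-grade inversion does not depend on an immune cause.

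Finally, the table is headed as guidelines, treatment responsibility rests with the investigator (section 7.0), and many investigators would wait for grade 1 anyway. The case that can be shown cleanly is narrow, and the counts above are upper bounds on those affected. This limits the size of the problem, but the written rule still allows the early restart.

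**Conclusion.** The concern holds. On the face of Table 2 the restart ceiling is grade 1 after worst grade 2 diarrhea and grade 2 after worst grade 3, and nothing in the available text removes this in cycle 1. It is a patient-safety inconsistency in individual cases, partly offset by the one-level reduction. It has no bearing on the primary endpoint rules, sample size or error rates.

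The number affected is likely to be small. The 2% to 10% rate is my assumption. The conclusion also rests on Table 2 being read literally by worst grade, and on Appendix II being unavailable for checking. The point should be corrected because the rule as written is out of order and the correction is cheap.

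**What to change.** Add one row to Table 2 for grade 3 diarrhea:

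- **Action:** the same hold condition as the grade 2 row (immune cause excluded or treated, and recovery to grade 1 or less).
- **Restart dose:** one dose level lower if the event is related to CFI-400945.

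Unrelated cases stay under the existing rule that doses change only for CFI-400945-related toxicity. The grade 2 row, the catch-all rows and the general restart sentence can remain as they are. Recovery to grade 1 also satisfies the general sentence, so no new conflict arises.

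The cost is one table row in an amendment, with no extra visits or tests. The downside is an occasionally longer hold for the few patients who would otherwise restart at grade 2. Some of them might then reach the 21-day limit and stop CFI-400945 permanently; the grade 2 row already carries that limit.

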7.1.6 Dose Adjustments – Durvalumab

The major toxic effects of durvalumab which are anticipated to limit dosing are hypersensitivity/infusion related reactions and possible class related immune related AEs, based on the mechanism of action of durvalumab leading to T-cell activation and proliferation. Potential immune related AEs across the class include pneumonitis, hepatitis, diarrhea/colitis and intestinal perforation, endocrinopathies (thyroiditis, hypo and hyperthyroidism, adrenal insufficiency, hypophysitis/hypopituitarism diabetes insipidus and Type 1 diabetes mellitus), nephritis, rash/dermatitis, pancreatitis, myocarditis, myositis/polymyositis and rare/less frequent irAEs including neuromuscular toxicities such as myasthenia gravis and Guillain-Barre syndrome. Other inflammatory responses that are rare with a potential immune-mediated etiology include, but are not limited to, pericarditis, sarcoidosis, uveitis and other events involving the eye (e.g. keratitis and optic neuritis), skin (e.g. scleroderma, vitiligo and pemphigoid), hematological (e.g. hemolytic anemia and immune thrombocytopenic purpura) and rheumatological (e.g. polymyalgia rheumatic and autoimmune arthritis) events, vasculitis, non infectious encephalitis or non infectious meningitis. It is possible that events with an inflammatory or immune mediated mechanism could occur in nearly all organs.

If a patient experiences several adverse events and there are conflicting recommendations, please use the recommended dose adjustment that requires the greatest dose hold or discontinuation. Adverse events will be graded using the NCI Common Terminology Criteria for Adverse Events (CTCAE) (see Appendix V).

Dose adjustments (slowing/interruption of infusion rate, omission of a dose, or permanent discontinuation) will be made for durvalumab- related adverse events.

If the infusion cannot be administered, it should be omitted until the next planned infusion.

The next cycle should not be given until the laboratory criteria in Section 4.1.8 are met and resolution of drug related toxicity, as detailed in Appendix II. For patients who have discontinued CFI-400945 and are continuing on durvalumab alone, criteria for creatinine clearance may be lower*. Please contact CCTG to discuss.

* For patients with low platelet counts that are not believed to be related for durvalumab please contact CCTG to discuss.

7.1.7 Management of Toxicity

See Appendix II for full details of toxicity management.

The following general guidance should be followed for management of toxicities:

1. Treat each of the toxicities with maximum supportive care (including slowing / interrupting / omitting the agent suspected of causing the toxicity where required).
2. If the symptoms promptly resolve with supportive care, consideration should be given to continuing the same dose of durvalumab along with appropriate continuing supportive care.
3. All dose modifications should be documented with clear reasoning and documentation of the approach taken.

In addition to the detailed toxicity management guidelines described in Appendix II, the following are recommended:

- Patient evaluation to identify any alternative etiology.
- In the absence of a clear alternative etiology, all events of an inflammatory nature should be considered to be immune-related.
- Symptomatic and topical therapy should be considered for low-grade events.
- For persistent (greater than 2 to 3 days) low-grade (Grade 2) or severe (Grade ≥ 3) events promptly start prednisone PO 1-2 mg/kg/day or IV equivalent.
- If symptoms recur or worsen during corticosteroid tapering (≥ 4 weeks of taper), increase the corticosteroid dose (prednisone dose [e.g. up to 2-4 mg/kg/day or IV equivalent]) until stabilization or improvement of symptoms, then resume corticosteroid tapering at a slower rate.
- More potent immunosuppressives (refer to individual sections of the immune related adverse event for specific type of immunosuppressive) should be considered for events not responding to systemic steroids.
- Discontinuation of study drug is not mandated for Grade 3 / Grade 4 inflammatory reactions attributed to local tumour response (e.g. inflammatory reaction at sites of metastatic disease, lymph nodes etc.). Continuation of study drug in this situation should be based upon a benefit/risk analysis for that patient and be discussed with CCTG.

7.1.8 Management of Infusion Reactions

Guidelines for management of infusion-related reaction are summarized in Appendix II. The standard infusion time for durvalumab is 1 hour. However, if there are interruptions during infusion, the total allowed time should not exceed 8 hours at room temperature.

Study personnel must be trained to recognize and treat anaphylaxis. The study site must have immediate access to appropriate drugs and medical equipment to treat acute anaphylactic reactions, emergency resuscitation teams and equipment in addition to the ability to admit patients to an intensive care unit if necessary.

7.1.9 Dose Adjustments for Immune Related Adverse Events and Other (Non-Immune Related) Adverse Events Related to Study Therapy

Guidelines for dose modification and toxicity management of immune related and non-immune related adverse events are summarized in Appendix II.

Centres must contact CCTG in the event of severe event(s), especially when the use of drugs such as infliximab are considered.

7.1.10 Duration of Therapy

Treatment will continue until the criteria for removal from protocol treatment have been met (see Section 10).

7.1.11 Patient Compliance

Treatment compliance will be monitored by drug accountability, as well as recording drug administration in the patient's medical record and case report form (CRF).

7.2 Concomitant Therapy

7.2.1 Permitted

- Other supportive and palliative care (e.g. pain control) as required throughout the study.
- Bone-targeted therapy for patients with bone metastases (bisphosphonates or denosumab).
- Anti-emetics or anti-diarrheal agents as required.
- Growth factors may be used according to centre policy to treat life threatening toxicity but cannot be used in place of protocol defined dose adjustments or prophylactically. Please consult CCTG in the case of patients experiencing multiple delays/omissions as exceptions may be made for patients who are benefitting from protocol therapy.

7.2.2 Not Permitted

- Administration of any other anti-cancer therapy is not permitted while the patient is receiving protocol therapy. Thereafter, patients may be treated at the investigator's discretion.
- Concurrent radiation treatment. (Note: if patients require palliative radiation or prophylactic radiation (e.g. of brain) consult CCTG for exception to this rule; protocol therapy will need to be held prior to and during the radiation.)
- Cytokines.
- Corticosteroids IV or PO (except for the treatment of \geq grade 3 infusion reaction, or treatment-related toxicity (See Appendix II). Note: Topical applications (e.g. rash), inhaled sprays (e.g. obstructive airways diseases), eye drops or local injections (e.g. intra-articular) are allowed, as are oral dose of steroids equivalent to 10 mg or less of prednisone.
- Live attenuated vaccines within 30 days of durvalumab dosing (i.e. 30 days prior to the first dose, during treatment with durvalumab and for 30 days post discontinuation of durvalumab). Inactivated vaccines, such as the injectable influenza vaccine, are permitted
- Drugs listed in Appendix VI Table 1 are not permitted during the study. Drugs listed in Appendix VI Table 2 should be used with caution only when it is absolutely necessary.

8.0 CRITERIA FOR MEASUREMENT OF STUDY ENDPOINTS

8.1 Definitions

8.1.1 Evaluable for Adverse Events

All patients will be evaluable for adverse event evaluation from the time of their first treatment.

8.1.2 Evaluable for Response

All patients who have received at least one cycle of therapy and have their disease re-evaluated will be considered evaluable for response. Patients who exhibit objective disease progression prior to the end of cycle 1 are considered to be evaluable. Patients on therapy for at least this period and who meet the other listed criteria will have their response classified according to the definitions set out below [Eisenhauer 2009].

Response and progression will be evaluated in this study using the revised international criteria (1.1) proposed by the RECIST (Response Evaluation Criteria in Solid Tumours) committee as well as the modified iRECIST guidelines [Seymour 2017]. Investigators should note the different requirements for confirmatory scans as well as follow up for the two criteria.

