8.2.5 Response

All patients will have their BEST RESPONSE from the start of study treatment until the end of treatment classified as outlined below:

Complete Response (CR): disappearance of *target* and *non-target* lesions and normalization of tumour markers. Pathological lymph nodes must have short axis measures < 10 mm (Note: continue to record the measurement even if < 10 mm and considered CR). Residual lesions (other than nodes < 10 mm) thought to be non-malignant should be further investigated (by cytology specialized imaging or other techniques as appropriate for individual cases [*Eisenhauer 2009*]) before CR can be accepted. Confirmation of response is required.

Partial Response (PR): at least a 30% decrease in the sum of measures (longest diameter for tumour lesions and short axis measure for nodes) of target lesions, taking as reference the baseline sum of diameters. Non target lesions must be non-PD. Confirmation of response is required.

Stable Disease (SD): Neither sufficient shrinkage to qualify for PR nor sufficient increase to qualify for PD taking as reference the smallest sum of diameters on study.

Progressive Disease (PD): at least a 20% increase in the sum of diameters of measured lesions taking as references the smallest sum of diameters recorded on study (including baseline) AND an absolute increase of ≥ 5 mm. Appearance of new lesions will also constitute progressive disease (including lesions in previously unassessed areas). In exceptional circumstances, unequivocal progression of non-target disease may be accepted as evidence of disease progression, where the overall tumour burden appears to have increased by at least 73% in volume or, in select instances where tumour burden has increased sufficiently to require urgent medical intervention (e.g. radiation for spinal cord compression or drainage of a fluid collection). Modest increases in the size of one or more non-target lesions are NOT considered unequivocal progression. If the evidence of PD is equivocal (target or non-target), treatment may continue until the next assessment, but if confirmed, the earlier date must be used.

Table 1: Integration of Target, non-Target and New Lesions into Response Assessment:

Target Lesions	Non-Target Lesions	New Lesions	Overall Response	Best Response for this Category also Requires
Target lesions ± non target lesions				
CR	CR	No	CR	Normalization of tumour markers, tumour nodes < 10 mm
CR	Non-CR/Non-PD	No	PR	
CR	Not all evaluated	No	PR	

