Non-iUPD/PD	Non-iUPD/PD	Yes	iUPD	Remains iUPD unless iCPD confirmed based on - increase in size or number of new lesions previously identified

* Using RECIST 1.1 principles. If no PSPD occurs, RECIST 1.1 and iRECIST categories for CR, PR and SD would be the same.
 ** In any lesion category.
 *** Previously identified in assessment immediately prior to this TP.

Table 3: iRECIST Best Overall Response (iBOR)

All patients will have their iBOR from the start of study treatment until the end of treatment classified as outlined below.

TPR1	TPR2	TPR3	TPR4	TPR5	iBOR
iCR	iCR, iPR, iUPD, NE	iCR, iPR, iUPD, NE	iUPD	iCPD	iCR
iUPD	iPR, iSD, NE	iCR	iCR, iPR, iSD, iUPD, NE	iCR, iPR, iSD, iUPD, iCPD, NE	iCR
iUPD	iPR	iPR, iSD, iUPD, NE	iPR, iSD, iUPD, NE, iCPD	iPR, iSD, iUPD, NE, iCPD	iPR
iUPD	iSD, NE	PR	iPR, iSD, iUPD, NE	iPR, iSD, iUPD, iCPD, NE	iPR
iUPD	iSD	iSD, iUPD, NE	iSD, iUPD, iCPD, NE	iSD, iUPD, ICPD, NE	iSD
iUPD	iCPD	Anything	Anything	Anything	iCPD
iUPD	iUPD	iCPD	Anything	Anything	iCPD
iUPD	NE	NE	NE	NE	iUPD

- Table assumes a randomized study where confirmation of CR or PR is not required.
- NE = not evaluable that cycle.
- Designation “I” for BOR can be used to indicate prior iUPD to aid in data interpretation.
- For patients with non-target disease only at baseline, only CR or non-CR/non-PD can be assigned at each TPR but is not shown in the table for ease of presentation.

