13.1 Primary Endpoints and Analysis

The primary endpoint of this study is objective response rate, which will be estimated by the proportion of evaluable patients who had complete response (CR) or partial response (PR) as their best response as assessed by RECIST 1.1 criteria. The exact 95% confidence interval for the response rate will be calculated. The median and range of the duration of response, defined as the time from date of CR or PR to the date when progression or death is observed, will be estimated based on Kaplan-Meier method.

Secondary objectives include Disease Control Rate (DCR, defined as CR or PR or stable disease (SD) > 16 weeks in duration) which will be analyzed similarly as objective response rate, as well as response rate determined by iRECIST.

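### The primary response rate, its exact confidence interval and DCR omit treated patients who are not evaluable, so they read high whenever such non-responders and at least one responder exist

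*Combined protocol and SAP*

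**What the plan says.** Section 13.1 says the primary ORR will be "estimated by the proportion of evaluable patients who had complete response (CR) or partial response (PR) as their best response". It adds: "The exact 95% confidence interval for the response rate will be calculated". DCR is a secondary endpoint, "which will be analyzed similarly as objective response rate". The iRECIST response rate is listed as secondary with no denominator of its own.

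Section 8.1.2 defines the evaluable set: "All patients who have received at least one cycle of therapy and have their disease re-evaluated will be considered evaluable for response". One group is added back: "Patients who exhibit objective disease progression prior to the end of cycle 1 are considered to be evaluable". Classification follows the same limits: "Patients on therapy for at least this period and who meet the other listed criteria will have their response classified" according to the definitions in the rest of Section 8.

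Section 13.2 states the Simon minimax rule on patients accrued. Fifteen are entered in stage 1, and the trial stops with 2 or fewer responses. Otherwise accrual continues to 28, and the null of 15% is rejected with 8 or more responses. The section does not say how a non-evaluable patient counts towards the 15 or the 28. No section gives an all-treated ORR, counts non-evaluable patients as non-responders, or provides for replacing them.

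**The concern.** The patients who fall outside Section 8.1.2 are not a random subset. A cycle lasts 28 days (Section 7.1.1) and imaging is every 8 weeks (Section 5.0), so the first scheduled scan comes well after cycle 1. There are two routes out of the denominator:

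- **No re-evaluation.** A treated patient dies, withdraws or declines before the first scan. The note to Table 1 in Section 8.2.5 says that symptomatic deterioration is not objective progression, so the early-progression exception does not bring such a patient back.
- **No completed cycle.** A patient stops all treatment in cycle 1 without objective progression. This patient fails the one-cycle condition even if scanned later. Section 7.1.5 foresees stopping CFI-400945 in cycle 1, and Section 7.1.1 starts durvalumab only in cycle 2.

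Apart from withdrawals for unrelated reasons, these are treatment failures. Leaving them out shifts the estimate, both confidence limits and DCR upwards. In a single-arm trial the reported ORR and its interval are what readers will set against the 15% benchmark. They would describe a selected subset, while the decision rule counts accrued patients.

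**Working it through.** **1. Reproduce the design (Section 13.2).** Inputs: 15 patients in stage 1, stop at 2 or fewer responses; 28 in total, reject at 8 or more; null 0.15, alternative 0.35.

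P(reject | p) = sum over x = 3 to 15 of P(Bin(15, p) = x) × P(Bin(13, p) ≥ max(0, 8 - x))

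- p = 0.15: 0.0461, within the stated 5%.
- p = 0.35: 0.8027, matching the stated 0.8.
- Probability of stopping at stage 1 when p = 0.15: 0.604.

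An exhaustive search gives 28 as the smallest total meeting 5% and 80%. The design is sound. When it is applied to accrued patients, someone with no assessment contributes no response, so these figures hold whatever the number of non-evaluable patients.

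**2. Effect on the reported rate.** Let N be the number treated, x the responders and k the treated non-responders who are not evaluable.

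Reported ORR / all-treated ORR = [x/(N-k)] / [x/N] = N/(N-k), for x ≥ 1

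If k = 0 the two rates agree. If x = 0 both are zero.

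**3. Size at the full 28.** The documents give no rate for k, so k = 1 to 4 is assumed. Limits are Clopper-Pearson: lower = 0.025 quantile of Beta(x, n-x+1), upper = 0.975 quantile of Beta(x+1, n-x), with n = 28 - k and x = 8.

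| k | n | 28/(28-k) | 8/n | Exact 95% CI |
|---|---|---|---|---|
| 0 | 28 | 1.00 | 28.6% | 13.2 to 48.7 |
| 1 | 27 | 1.04 | 29.6% | 13.8 to 50.2 |
| 2 | 26 | 1.08 | 30.8% | 14.3 to 51.8 |
| 3 | 25 | 1.12 | 32.0% | 14.95 to 53.5 |
| 4 | 24 | 1.17 | 33.3% | 15.6 to 55.3 |

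At k = 4 the lower limit passes 15%; at k = 3 it is still just below. Eight of 28 already rejects under the Simon rule, so this crossing changes how the interval reads and not the decision.

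**4. Estimate against decision.** Seven responders among 28 fail the rule (7/28 = 25.0%). With k = 4 they would be reported as 7/24 = 29.2%, higher than the smallest success on all 28 (8/28 = 28.6%).

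**5. If the trial stops at stage 1.** Here N = 15 and the factor is larger: 15/14 = 1.07 at k = 1 and 15/13 = 1.15 at k = 2. Two responders read as 14.3% or 15.4% instead of 2/15 = 13.3%.

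**6. The same factor applies to DCR**, with x the number of controlled patients and k the non-evaluable patients without documented control.

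**The case against.** The evaluable-only analysis is prespecified, and several provisions keep k small. Objective early progressors stay in. Imaging follows the calendar even when cycles slip (Section 5.0, footnote 12), and assessments are to continue until progression (Section 8.2). Follow-up is sought after treatment stops (Section 10.1 and the Table 1 note), and one agent may continue without the other (Section 10.2). Entry requires ECOG 0 or 1 and a life expectancy of 3 months or more (Sections 4.1.6 and 4.1.7). The nearest figure for early loss is 2 of 50 phase I patients stopping for possibly related adverse events (Section 3.1.3): 4%, or about 1 of 28. At k = 1 the ORR moves by one percentage point inside an interval about 35 points wide.

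This limits the size and leaves the gap open. Those provisions govern data collection, and none says how to count a patient with no scan. The phase I figure covers any time on study and omits deaths and deterioration, so it is not a non-evaluability rate.

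A reader might infer three stronger points that the documents do not support:

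- **That the type I error is inflated.** This would need non-evaluable patients to be replaced or left out of the count of 28. Section 13.2 speaks of accrued patients, and there is no replacement rule. The word accrued favours counting everyone but does not settle the matter, because Section 13.1 defines the response rate among evaluable patients. What can be said is that Section 13.2 leaves the set undefined.
- **That Section 8 already requires an all-patient denominator.** Section 8.2.5 says "All patients will have their BEST RESPONSE from the start of study treatment until the end of treatment classified as outlined below", and Section 8.3 says "All patients will have their iBOR from the start of study treatment until the end of treatment classified as outlined below". Both can be read as the definitions to which Section 8.1.2 sends its evaluable patients. Neither sets a denominator, and neither treats the not-evaluable category as non-response.
- **That the rate is always too high.** It is not if k = 0 or nobody responds. A patient who stopped within cycle 1 and was later scanned as responding would also be excluded, which pulls the other way, but this should be unusual.

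**Conclusion.** The point holds as a matter of estimation and reporting. Following Sections 8.1.2 and 13.1 as written, the primary ORR, its exact interval and DCR omit treated patients who are mostly likely to be failures. With at least one responder and k ≥ 1 such non-responders, the ORR is overstated by the factor N/(N-k), with N = 28, or 15 after a stage 1 stop. For an assumed k of 1 to 4 of 28 the factor is 1.04 to 1.17, or 1.1 to 4.8 percentage points at eight responders. The direction follows from the text; the size rests on the assumed k. The go/no-go rule applied to accrued patients keeps its type I error of 0.046 and power of 0.803.

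It should be fixed before analysis. Whether the patients enrolled at earlier starting doses (Section 3.1.4) belong to the 28 is a separate question and does not bear on this conclusion.

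**What to change.** - **Sections 13.1 and 8.1.2:** make the primary denominator for ORR, DCR and the iRECIST rate all patients who received at least one dose and are counted in the Section 13.2 rule. Count those without a post-baseline assessment as non-responders.
- **Section 13.2:** state that the 2/15 and 8/28 boundaries apply to that same set. State also that an enrolled patient who is never dosed is outside it and does not use one of the 15 or 28 places. The enrolment limit of 28 in the introductory summary should then be worded in the same terms.
- **Sensitivity analysis:** report the evaluable-only rate, with the number of non-evaluable patients and the reasons.

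The cost is a few sentences. No new data are needed, and no extra patients beyond filling the place of anyone never dosed. The downside is a slightly less favourable reported ORR.
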